3.6 Post Study Drug Follow up

In this study, *OS is the primary endpoint of the study*. Post treatment follow-up is thus of critical importance and is essential to preserving subject safety and the integrity of the study. Subjects who discontinue study drug must continue to be followed for collection of outcome and/or survival follow-up data as required and in line with [Table 5.1-3](#) until death or the conclusion of the study. Subjects who discontinue study drug will continue to be followed.

BMS may request that survival data be collected on all treated/randomized subjects outside of the 3 month (\pm 14 days) specified visit schedule. At the time of this request, each subject will be contacted to determine their survival status unless the subject has withdrawn consent for all contact.

3.6.1 Withdrawal of Consent

Subjects who request to discontinue study drug will remain in the study and must continue to be followed for protocol specified follow-up procedures. The only exception to this is when a subject specifically withdraws consent for any further contact with him/her or persons previously authorized by subject to provide this information. Subjects should notify the investigator of the decision to withdraw consent from future follow-up **in writing**, if possible. The withdrawal of consent should be explained in detail in the medical records by the investigator, as to whether the withdrawal is from further treatment with study drug only or also from study procedures and/or post treatment study follow-up, and entered on the appropriate CRF page. In the event that vital status (whether the subject is alive or dead) is being measured, publicly available information should be used to determine vital status only as appropriately directed in accordance with local law.

3.6.2 *Lost to Follow-Up*

All reasonable efforts must be made to locate subjects to determine and report their ongoing status. This includes follow-up with persons authorized by the subject as noted above. Lost to follow-up is defined by the inability to reach the subject after a minimum of three documented phone calls, faxes, or emails as well as lack of response by subject to one registered mail letter. All attempts should be documented in the subject's medical records. If it is determined that the subject has died, the site will use permissible local methods to obtain the date and cause of death.

If investigator's use of third-party representative to assist in the follow-up portion of the study has been included in the subject's informed consent, then the investigator may use a Sponsor-retained third-party representative to assist site staff with obtaining subject's contact information or other public vital status data necessary to complete the follow-up portion of the study. The site staff and representative will consult publicly available sources, such as public health registries and databases, in order to obtain updated contact information. If after all attempts, the subject remains lost to follow-up, then the last known alive date as determined by the investigator should be reported and documented in the subject's medical records.

4 STUDY DRUG

Study drug includes both Investigational [Medicinal] Product (IP/IMP) and Non-investigational Medicinal Product (Non-IP/Non-IMP) and can consist of the following:

Table 4-1: Study Drugs for CA209498

Product Description / Class and Dosage Form	Potency	IP/Non-IMP	Blinded or Open Label	Packaging/ Appearance	Storage Conditions (per label)
Nivolumab BMS-936558-01 Solution for Injection ^a	100 mg (10 mg/mL)	IP	Open-label	10 mL per vial (5 or 10 vials/carton Clear to opalescent colorless to pale yellow liquid. May contain particles	2 to 8°C. Protect from light and freezing
Temozolomide Capsules ^b	20 mg	IP	Open-label	Wallet/blister card containing 5 capsules White opaque cap and body, imprinted in yellow ink. The cap is imprinted with '891.' The body is imprinted with '20 mg' and two stripes.	Do not store above 25 °C.
Temozolomide Capsules ^b	100 mg	IP	Open-label	Wallet/blister card containing 5 capsules White opaque cap and body, imprinted in pink ink. The cap is imprinted with '892.' The body is imprinted with '100 mg' and two stripes.	Do not store above 25 °C.
Temozolomide Capsules ^b	140 mg	IP	Open-label	Wallet/blister card containing 5 capsules White opaque cap and body, imprinted in blue ink. The cap is imprinted with '929'. The body is imprinted with '140 mg' and two stripes.	Do not store above 25 °C.

^a May be labeled as either “BMS-936558-01” or “Nivolumab”

^b These products may be obtained by the investigational sites as local commercial product in certain countries if allowed by local regulations. In these cases, products may be a different pack size/potency than listed in the table. These products should be prepared/stored/administered in accordance with the package insert or summary of product characteristics (SmPC).

4.1 Investigational Product

An investigational product, also known as investigational medicinal product in some regions, is defined a pharmaceutical form of an active substance or placebo being tested or used as a reference in a clinical study, including products already with a marketing authorization but used or assembled (formulated or packaged) differently than the authorized form, or used for an unauthorized indication, or when used to gain further information about the authorized form.

The investigational product should be stored in a secure area according to local regulations. It is the responsibility of the investigator to ensure that investigational product is only dispensed to study subjects. The investigational product must be dispensed only from official study sites by authorized personnel according to local regulations. Although not a medicinal product, Radiation Therapy is also considered part of study treatment.

In this protocol, investigational products are:

- BMS-936558 (nivolumab)
- Temozolomide

4.2 Non-Investigational Product

Other medications used as support or escape medication for preventative, diagnostic, or therapeutic reasons, as components of the standard of care for a given diagnosis, may be considered as non-investigational products.

See [Section 4.5](#) for details regarding study drug dosing in combination with RT.

4.3 Storage of Study Drug

The product storage manager should ensure that the study drug is stored in accordance with the environmental conditions (temperature, light, and humidity) as determined by BMS. If concerns regarding the quality or appearance of the study drug arise, the study drug should not be dispensed and contact BMS immediately.

Study drug not supplied by BMS will be stored in accordance with the package insert.

Please refer to [Section 9.2.2](#) for guidance on IP records and documentation.

Infusion-related supplies (eg, IV bags, in-line filters (0.2-1.2 micron), 0.9% NaCl or 5% Dextrose solution) will not be supplied by the sponsor and should be purchased locally if permitted by local regulations.

For non-investigational product, if marketed product is utilized, it should be stored in accordance with the package insert, summary of product characteristics (SmPC), or similar.

Please refer to the current version of the Investigator Brochure and/or pharmacy reference sheets for complete storage, handling, dispensing, and infusion information for BMS-936558 (nivolumab).⁵¹

4.3.1 Nivolumab (BMS-936558)

For details regarding drug storage, preparation, administration, and use time please refer to the BMS-936558 (nivolumab) Investigator Brochure and/or pharmacy reference sheets.

4.3.2 Temozolomide

For countries in which BMS is providing packaged/labeled temozolomide, please refer to package insert, summary of product characteristics (SmPC), or similar document for details regarding drug preparation, administration and use time.

For countries where local sourcing of temozolomide is permitted, product should be stored, prepared and administered in accordance to the package insert, summary of product characteristics (SmPC) or similar document.

4.4 Method of Assigning Subject Identification

After informed consent has been obtained, the subject must be enrolled into the study by calling an IVRS to obtain the subject number. Every subject that signs the informed consent form must be assigned a subject number in IVRS. The investigator or designee will register the subject for enrollment by following the enrollment procedures established by BMS. The following information is required for enrollment:

- Date that informed consent was obtained
- Date of birth of subject
- Gender (at birth) of subject

CA209498 is a randomized study. Central lab confirmation of MGMT un-methylated status must be received prior to the IVRS randomization call. Once enrolled in IVRS, enrolled subjects who meet all eligibility criteria, and are clinically ready to begin treatment, will be randomized through the IVRS. The following information is required for randomization:

- Subject number
- Date of birth of subject
- Extent of tumor resection: Complete or Partial

Subjects meeting all eligibility criteria will be randomized in a 1:1 ratio to receive radiotherapy + nivolumab (RT+ nivolumab) or radiotherapy + temozolomide (RT + TMZ). MGMT methylation status will be transferred from the testing laboratory to the IVRS database.

The exact procedures for using the IVRS will be detailed in the IVRS manual.

4.5 Selection and Timing of Dose for Each Subject

Dosing schedules for both arms are detailed in [Table 4.5-1](#). All subjects will undergo surgical resection and radiotherapy as outlined in [Sections 3.1](#). For the RT + nivolumab arm, the first dose of nivolumab is to be administered within 7 days of randomization. For the RT + TMZ arm, the first dose of temozolomide is to be administered at the beginning of radiotherapy. Treatment details

are described separately for each arm below; treatment modifications (eg, dose delay, reduction, or discontinuation) will be based on specific laboratory and AE criteria, as described in Sections 4.5.1 and 4.5.2.

Table 4.5-1: Selection and Timing of Dose

Drug	Dose	Frequency of administration	Route of administration	Duration
Arm RT + Nivolumab (BMS-936558)	240 mg, then 480 mg after 8 doses	Every 2 weeks, for 8 doses, then Every 4 weeks after 8 doses	30 minute intravenous (IV)	Until progression, unacceptable toxicity, or discontinuation from treatment
Arm RT + TMZ (Temozolomide)	75 mg/m ² daily during RT then 150 mg/m ² D1-5 for C1 and increased to 200 mg/m ² D1-5 for C2-C6 as tolerated	Daily from first day of RT to last day of RT (not to exceed 49 days) then 4 week break followed by TMZ daily for 5 days every 28 days x 6 cycles ^a	Oral (PO)	Until completion of dosing, progression, unacceptable toxicity or discontinuation from treatment

^a Additional cycles of temozolomide are permitted for subjects enrolled in Japan

4.5.1 Nivolumab Dosing

4.5.1.1 Nivolumab Dose and Schedule

Subjects randomized to nivolumab should begin treatment within 7 days of randomization, but RT should begin within 42 days after definitive resection, but may be delayed if clinically required. Subjects will continue on study treatment until progression, unacceptable toxicity, withdrawal of consent, or the study ends, whichever comes first.

Subjects randomized to the RT + nivolumab arm will begin nivolumab at a dose of 240 mg, given as a 30-minute IV infusion on Day 1 of each treatment cycle Q2W for 8 doses. The nivolumab dose will then change to 480 mg as a 30-minute IV infusion Q4W with dose 9 (starting week 17, in the absence of delays). Nivolumab injection can be infused undiluted or diluted so as not to exceed a total infusion volume of 120 mL. Nivolumab infusion must be promptly followed by a saline flush to clear the line.

Continuation of nivolumab treatment with suspected progression is permitted, see Section 4.5.1.6. Treatment will continue until discontinuation from study treatment for any of the criteria listed in sections 3.5 or 4.5.1.5.

There will be no dose escalations or reductions of nivolumab allowed. Subjects may be dosed no less than 12 days from the previous dose during Q2W cycles. A dose given more than 3 days after the intended dose will be considered a delay. For Q4W dosing cycles, subjects may be dosed within a ± 3 day window. Premedications are not recommended for the first dose of nivolumab.

Subjects should be monitored for infusion reactions during nivolumab administration. If an acute reaction is noted, subjects should be managed according to [Section 4.5.1.8](#).

Doses of nivolumab may be interrupted, delayed or discontinued depending on how well the subject tolerates treatment. Dosing visits are not skipped, only delayed. Nivolumab should be delayed (see [Section 4.5.1.3](#)) for toxicities considered at least possibly-related to nivolumab. Nivolumab interruption refers to stopping the infusion, eg, for an infusion reaction (see [Section 4.5.1.8](#)).

No incompatibilities have been observed between nivolumab for injection and polyvinyl chloride (PVC), non-PVC/non-DHEP (di(2ethylhexyl)phthalate) IV components or glass bottles. Instructions for dilution and infusion of nivolumab injection may be provided in the clinical protocol, pharmacy binder, or pharmacy reference sheet. Care must be taken to assure sterility of the prepared solution because the product does not contain any antimicrobial preservative or bacteriostatic agent.

4.5.1.2 Dose Modifications for Nivolumab

Dose modification is not allowed for nivolumab; for dose delay, see [4.5.1.3](#).

4.5.1.3 Dose Delay Criteria for Nivolumab

Tumor assessments should continue per protocol schedule, even if dosing is delayed.

Nivolumab administration should be delayed for the following:

- Grade 2 non-skin, drug-related AE, with the exception of fatigue
- Grade 2 drug-related creatinine, AST, ALT, and/or total bilirubin abnormalities
- Grade 3 skin drug-related AE
- Grade 3 drug-related laboratory abnormality with the following exceptions:
 - Grade 3 lymphopenia or asymptomatic amylase or lipase does not require dose delay
 - Grade ≥ 3 ALT/AST or total bilirubin will require dose discontinuation (see [Section 4.5.1.5](#))
- Any AE, laboratory abnormality, or intercurrent illness which, in the judgment of the investigator, warrants delaying the dose of study medication.

Subjects who require delay of nivolumab should be re-evaluated weekly or more frequently if clinically indicated. Nivolumab dosing can be resumed on the established dosing schedule (q2 or q4 weeks) when retreatment criteria are met ([Section 4.5.1.4](#)).

4.5.1.4 Criteria to Resume Dosing for Nivolumab

Subjects may resume treatment with study drug when the drug-related AE(s) resolve to Grade ≤ 1 or baseline value, with the following exceptions:

- Subjects may resume treatment in the presence of Grade 2 fatigue
- Subjects who have not experienced a Grade 3 drug-related skin AE may resume treatment in the presence of Grade 2 skin toxicity

- For subjects with Grade 2 AST, ALT, and/or total bilirubin abnormalities, dosing may resume when laboratory values return to baseline and management with corticosteroids, if needed, is complete.
- Subjects with combined Grade 2 AST/ALT AND total bilirubin values meeting discontinuation parameters (Section 4.5.1.5) should have treatment permanently discontinued.
- Drug-related pulmonary toxicity, diarrhea or colitis must have resolved to baseline before treatment is resumed. Subjects with persistent Grade 1 pneumonitis after completion of a steroid taper over at least 1 month may be eligible for retreatment if discussed with and approved by BMS Medical Monitor (or designee).
- Subjects with drug-related endocrinopathies adequately controlled with only physiologic hormone replacement may resume treatment after consultation with the BMS Medical Monitor (or designee). Adrenal insufficiency requires discontinuation regardless of control with hormone replacement.

4.5.1.5 Treatment Discontinuation Criteria for Nivolumab

Nivolumab treatment should be permanently discontinued for the following:

- Any Grade 2 drug-related uveitis, eye pain or blurred vision that does not respond to topical therapy and does not improve to Grade 1 severity within the re-treatment period OR requires systemic treatment.
- Any Grade 3 non-skin, drug-related AE lasting > 7 days or recurs, with the following exceptions for laboratory abnormalities, drug-related uveitis, pneumonitis, bronchospasm, neurological toxicity, hypersensitivity reactions, infusion reactions, and endocrinopathies:
 - Grade 3 drug-related uveitis, pneumonitis, bronchospasm, neurological toxicity, hypersensitivity reaction, or infusion reaction of any duration requires discontinuation
 - Grade 3 drug-related endocrinopathies adequately controlled with only physiologic hormone replacement do not require discontinuation. Adrenal insufficiency requires discontinuation regardless of control with hormone replacement.
 - Grade 3 drug-related laboratory abnormalities do not require treatment discontinuation except:
 - ◆ Grade 3 drug-related thrombocytopenia > 7 days or associated with bleeding requires discontinuation
 - ◆ Grade ≥ 3 drug-related AST, ALT, or total bilirubin requires discontinuation*
*In most cases of Grade 3 AST or ALT elevation, study drug(s) will be permanently discontinued. If the investigator determines a possible favorable benefit/risk ratio that warrants continuation of study drug(s), a discussion between the investigator and the BMS Medical Monitor/designee must occur.
 - ◆ Concurrent AST or ALT > 3 x ULN and total bilirubin > 2 x ULN

- Any Grade 4 drug-related AE or laboratory abnormality (including but not limited to creatinine, AST, ALT, or total bilirubin), except for the following events which do not require discontinuation:
 - Grade 4 neutropenia \leq 7 days
 - Grade 4 lymphopenia or leukopenia or asymptomatic amylase or lipase
 - Isolated Grade 4 electrolyte imbalances/abnormalities that are not associated with clinical sequelae and are corrected with supplementation/appropriate management within 72 hours of their onset.
 - Grade 4 drug-related endocrinopathy AEs, hyper- or hypothyroidism, or glucose intolerance, which resolve or are adequately controlled with physiologic hormone replacement (corticosteroids, thyroid hormones) or glucose-controlling agents, respectively, may not require discontinuation after discussion with and approval from the BMS Medical Monitor (or designee).
- Any event that leads to delay in dosing lasting $>$ 6 weeks from the previous dose requires discontinuation, with the following exceptions:
 - Dosing delays to allow for prolonged steroid tapers to manage drug-related AEs are allowed.
 - Dosing delays lasting $>$ 6 weeks from the previous dose that occur for non-drug-related reasons may be allowed, if approved by the BMS Medical Monitor (or designee).
 - Prior to re-initiating treatment in a subject with a dosing delay lasting $>$ 6 weeks, the BMS medical monitor (or designee) must be consulted. Tumor assessments should continue as per protocol even if dosing is delayed. Periodic study visits to assess safety and laboratory studies should also continue every 6 weeks or more frequently if clinically indicated during such dosing delays.
- Any AE, laboratory abnormality, or intercurrent illness which, in the judgment of the Investigator, presents a substantial clinical risk to the subject with continued nivolumab dosing.

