4.5.1.7 Management Algorithms for Immuno-Oncology Agents

Immuno-oncology (I-O) agents are associated with AEs that can differ in severity and duration than AEs caused by other therapeutic classes. Nivolumab is considered an immuno-oncology agent in this protocol. Early recognition and management of AEs associated with immuno oncology agents may mitigate severe toxicity. Management Algorithms have been developed to assist investigators in assessing and managing the following groups of AEs:

- Gastrointestinal
- Renal
- Pulmonary
- Hepatic
- Endocrinopathy
- Skin
- Neurological

The above algorithms are found in [Appendix 1](#) and in the nivolumab Investigator Brochure.

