7.1.1.3 Immune-Mediated Adverse Events

In order to further characterize AEs of special clinical interest analysis of immune-mediated AEs (IMAE) will be conducted. Immune-mediated AEs are specific events (or groups of PTs describing specific events) that include pneumonitis, diarrhea/colitis, hepatitis, nephritis/renal dysfunction, rash, endocrine (adrenal insufficiency, hypothyroidism/thyroiditis, hyperthyroidism, diabetes mellitus, and hypophysitis), and other specific events, considered as potential immune-mediated events by investigator, that meet the definition summarized below:

- those occurring within 100 days of the last dose,
- regardless of causality,
- treated with immune-modulating medication (of note, endocrine AEs such as adrenal insufficiency, hypothyroidism/thyroiditis, hyperthyroidism, diabetes mellitus, and hypophysitis are considered IMAEs regardless of immune-modulating medication use, since endocrine drug reactions are often managed without immune-modulating medication).
- with no clear alternate etiology based on investigator assessment, or with an immune-mediated component

The list of MedDRA preferred terms used to identify Immune-Mediated adverse events is revisited quarterly and updated accordingly. The preferred terms used for the selection at the time of the database lock by categories will be provided.

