7.5 Efficacy

Unless otherwise specified, the primary population will consist in the all randomized subjects and the analysis will be performed by treatment group as “randomized”.

Unless stated otherwise, whenever a stratified analysis is specified, the following stratification factors (recorded at randomization as per IRT) will be used:

- Extent of tumor resection (complete or partial)

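### The Grade 4 endocrinopathy exception for nivolumab omits the adrenal insufficiency exclusion that the protocol states in two other places

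*Protocol*

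**What the plan says.** Protocol 3.5 makes discontinuation mandatory for unacceptable toxicity and refers to 4.5.1.5 for the nivolumab criteria. Three provisions deal with endocrinopathies that hormone replacement controls:

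- **Protocol 4.5.1.4, resuming after a delay.** Controlled drug-related endocrinopathies may resume after Medical Monitor consultation. The next sentence reads "Adrenal insufficiency requires discontinuation regardless of control with hormone replacement". No grade is given.
- **Protocol 4.5.1.5, Grade 3 item.** Controlled Grade 3 endocrinopathies need not stop. The same adrenal insufficiency sentence follows, word for word, inside the Grade 3 sub-bullet.
- **Protocol 4.5.1.5, Grade 4 item.** Grade 4 drug-related events stop treatment unless listed as exceptions. One listed exception covers Grade 4 endocrinopathies that resolve or are "adequately controlled with physiologic hormone replacement (corticosteroids, thyroid hormones) or glucose-controlling agents, respectively, may not require discontinuation", subject to discussion with the Medical Monitor or designee and their approval. The adrenal insufficiency sentence does not appear.

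SAP 7.1.1.3 counts adrenal insufficiency among the endocrine events: "endocrine (adrenal insufficiency, hypothyroidism/thyroiditis, hyperthyroidism, diabetes mellitus, and hypophysitis").

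**The concern.** A mandatory stopping rule should give one answer for one event. Here two provisions say that adrenal insufficiency ends nivolumab whether or not it is controlled. A third, which applies to the more severe grade, allows approval to continue.

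A site and a Medical Monitor could follow the Grade 4 text in good faith and keep a subject on nivolumab after an event that the protocol elsewhere treats as an absolute stop. Two monitors could also decide the same case differently, each with protocol support. What is at stake is the safety of a small group of subjects, not the validity of the efficacy comparison.

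**Working it through.** The protocol states no figure on this point, so the check is a comparison of texts.

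**Step 1: does the Grade 4 exception reach adrenal insufficiency?** It covers drug-related endocrinopathies as a class and names corticosteroids as a physiologic replacement. The SAP classes adrenal insufficiency as endocrine. Nothing in the exception takes it out, so on its words it is included.

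**Step 2: apply the text grade by grade to drug-related adrenal insufficiency controlled on replacement.**

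| Grade | Provision | Result |
|---|---|---|
| 2 | 4.5.1.3 delays dosing for a "Grade 2 non-skin, drug-related AE, with the exception of fatigue"; 4.5.1.4 then applies | Held; may not resume |
| 3 | 4.5.1.5, Grade 3 endocrinopathy item | Must stop |
| 4 | 4.5.1.5, Grade 4 exception | May continue with Medical Monitor approval |

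The most severe grade gets the most lenient rule, and the documents give no reason for it.

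**Step 3: could the adrenal insufficiency sentence govern all grades?** It names no grade, so this reading is possible. However, in 4.5.1.5 it sits inside the Grade 3 item, and in 4.5.1.4 it sits among the criteria for resuming. Where 4.5.1.5 wants a rule to span grades it says so, as in the liver-test item set at Grade 3 or above. No order of precedence is stated in the text available. Either way there is a defect:

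- If the sentence covers all grades, the Grade 4 exception lets the Medical Monitor approve what the sentence forbids.
- If it covers Grade 3 only, severity and strictness run in opposite directions.

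**Step 4: how much of the gap do other provisions close?**

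- A site cannot continue on its own reading, because approval is required.
- Once a dose is held, 4.5.1.4 bars resumption at any grade. But 4.5.1.3 has no delay criterion for a Grade 4 endocrinopathy, so a hold depends on its discretionary item: "Any AE, laboratory abnormality, or intercurrent illness which, in the judgment of the investigator, warrants delaying the dose of study medication".
- Protocol 4.5.1.1 counts a dose as delayed when given more than 3 days late. The clear remaining case is therefore one that arises, is controlled and is approved before the next dose becomes late. That is at most 14 + 3 = 17 days after the previous dose on the two-weekly schedule, or 28 + 3 = 31 days on the four-weekly schedule.

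**Step 5: who is exposed?** Only the RT + nivolumab arm: 550 / 2 = 275 planned subjects at 1:1 randomization. This is the size of the arm, not the number at risk of the event.

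**Step 6: effect on the analysis.** SAP 7.5 says "the primary population will consist in the all randomized subjects and the analysis will be performed by treatment group as" randomized. Whether a subject stops or continues nivolumab does not change membership of the OS analysis or the arm in which the subject is counted.

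**The case against.** The best reply is that the texts can be reconciled. The adrenal insufficiency sentence is specific and mandatory; the Grade 4 exception is general and only permissive. Stopping nivolumab satisfies both. The exception also lifts only the any-Grade-4 criterion and need not cancel a stop required elsewhere. Naming corticosteroids proves little, since SAP 7.1.1.3 also lists hypophysitis, so the exception has work to do without adrenal insufficiency. The remaining gap is small and guarded by an approval step. Finally, Protocol 4.5.1.7 places the endocrinopathy algorithm in Appendix 1 "and in the nivolumab Investigator Brochure"; neither was available for review, and either might settle the matter.

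Much of this stands. The gap is narrow, no site can act alone, and the statement that no precedence is given holds only for the text available.

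The rest does not remove the problem. The specific-over-general reading must be supplied by the reader. The exception may have been written with other endocrine events in mind, but it does not exclude this one. The approval step is a weak safeguard here, because the Medical Monitor works from the same text, and that text grants discretion where the other two provisions leave none.

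**Conclusion.** The concern holds. The nivolumab stopping rule is inconsistent as written: two provisions require discontinuation for adrenal insufficiency however well controlled, and the Grade 4 exception permits approved continuation without excluding it.

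It is a limited patient-safety issue, worth correcting. It affects only drug-related Grade 4 adrenal insufficiency controlled on replacement in the RT + nivolumab arm, most clearly where no dose has been held. The documents give no frequency for that event, so no count of affected subjects can be offered. There is no effect on the OS analysis, type I error or power.

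The conclusion rests on treating adrenal insufficiency as an endocrinopathy, as the SAP does, and on the text available. The Appendix 1 algorithm and the Investigator Brochure were not seen.

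**What to change.** Add to the Grade 4 endocrinopathy exception in Protocol 4.5.1.5: *except adrenal insufficiency, which requires discontinuation at any grade*. This matches the rule the protocol already states twice.

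If the sponsor does intend to allow approved continuation, it should instead amend both adrenal insufficiency sentences, in 4.5.1.4 and in the Grade 3 item of 4.5.1.5, so that all three provisions agree. In either case, confirm that the Appendix 1 endocrinopathy algorithm gives the same instruction.

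The preferred change costs one clause at the next protocol revision. Data collection and the SAP need no change.
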